***Follow-Up Survey Only***

**TLFB (Sobell & Sobell, 1992).** The TLFB is a widely-used, semi-structured interview that uses a calendar to retrospectively collect daily information about substance use. It has been shown to have good reliability and validity and is widely considered the “gold standard” of quantity and frequency substance use assessment. To accommodate the remote study procedures, the TLFB was adapted from interviewer to computer administered (via REDCap), which has been found to be reliable and valid (e.g., Martin-Willett et al., 2020). The TLFB was used to obtain detailed past 28-days frequency of opioid pain medication and alcohol use information.

**Acceptability.** Participants were asked to answer questions about satisfaction, acceptability, and feasibility on a 0-10 scale based on those used in a previous RCT investigating an app developed for chronic pain patients (Jamison et al., 2017).

**Validity and Accuracy of Responses.** All participants were asked how honest they were in completing the daily survey (response options: I was very honest, I was honest most of the time, I was honest some of the time, I was honest once in a while, I was not honest at all). CM participants were additionally asked how much the rewards made a difference in how accurately

they reported information in the daily survey (response options: Not at all, very little, little, somewhat, much, to a great extent, completely).

**Self-Report of Impact of Behavioral Incentives to Adherence.** CM participants were asked how much the rewards made a difference in whether they completed the daily survey (response options: Not at all, very little, little, somewhat, much, to a great extent, completely).

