### ***Sample Size Justification***

As this is a Stage I pilot study and no preliminary data are available, a power analysis is not provided. Sample size was determined by anticipating a medium effect size (.05), 80% power, alpha level=.05 (Cohen, 1988). For two-sided *t*-tests, 32 participants/group are needed. This would allow us to detect an effect size of  $d=.711$ , which falls between medium,  $d=.05$  and large,  $d=.8$  effect sizes. Recruitment of 80 subjects with 80% retention was expected to achieve this effect size.

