### ***Outcome Measures***

As shown in Table 4, the primary outcome measures are the number of completed daily self-monitoring surveys and the longest period of sustained adherence to survey completion. It is hypothesized that those in the CM group will complete more daily self-monitoring surveys and have a longer sustained period of daily survey completion compared to controls. The number of completed daily surveys and duration of continuous daily survey completion will be compared between CM and Co groups using independent *t*-tests.

Secondarily, descriptive statistics will be used to summarize CM participants' self-report of the impact of behavioral incentives on adherence. Mean time to complete the daily surveys between CM and Co groups will be compared using an independent *t*-test. Pain experience and

related variables from baseline will be compared to follow up responses for the total sample using paired *t*-tests. The daily survey item responses will be summarized for the overall sample using descriptive statistics. Associations between daily survey and follow-up TFLB for alcohol and prescription opioid use data for the overall sample and each study group will be examined using Spearman's correlations. Descriptive statistics will be used to summarize self-report validity and accuracy of responses. Feasibility and acceptability of CM app implementation will be examined by comparing follow-up acceptability survey ratings for each group using independent *t*-tests.

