**Table 4**

*Outcome Measures Overview*

Name	Time Frame	Brief Description
Number of daily surveys completed	28-day daily survey period	This primary outcome is consistent with previous CM studies.
Longest period of sustained adherence to daily survey completion	28-day daily survey period	Largest number of consecutive days wherein daily surveys were completed. This primary outcome is consistent with previous CM studies.
Mean frequency of alcohol and prescription opioid use (days of use)	28-day daily survey period to follow up	Spearman's correlations between daily survey and TLFB data for alcohol and prescription opioid frequency (days of use) were conducted for the entire sample, the CM group, and the Co group.
Mean time to complete the daily surveys	28-day daily survey period	Daily survey completion time (the amount of time from daily survey start to finish).

Name	Time Frame	Brief Description
Mean CM app feasibility and acceptability survey ratings	Follow up	CM app satisfaction, acceptability, and feasibility survey ratings (on a 0-10 scale; administered at follow-up) based on those used in a previous RCT investigating an app developed for chronic pain patients (Jamison et al., 2017).
Self-report validity and accuracy of responses	Follow up	Ratings of how honest participants were in completing the daily survey and how much the rewards made a difference in how accurately CM participants reported information in the daily survey.

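### No between-arm estimate is planned for reporting accuracy: the honesty item is only summarised, and the survey-TLFB correlations by arm carry no difference or interval and also reflect survey completion

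*Combined protocol and SAP*

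**What the plan says.** The Introduction lists accuracy of prescription opioid and alcohol reporting among the secondary questions. Aim 3 is to examine agreement between the daily survey and the follow-up report in both groups; it carries no hypothesis. Table 4 lists one outcome that joins rated honesty with the effect of rewards on accuracy.

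Three measures bear on this:

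- **Honesty item (five ordered answers).** Under Follow-Up Survey Only: "All participants were asked how honest they were in completing the daily survey". It is therefore available in both arms.
- **Rewards-and-accuracy item.** Asked of CM participants only (same section, and item 11 of the Appendix B feedback questions).
- **Survey against TLFB.** Table 4 says that Spearman correlations of days of use "were conducted for the entire sample, the CM group, and the Co group".

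For the first two, the analysis text in Outcome Measures is: "Descriptive statistics will be used to summarize self-report validity and accuracy of responses". It does not say whether the summary is by arm. For the third, neither Outcome Measures nor Table 4 mentions a difference between arms or a confidence interval. The same section does name independent *t*-tests between arms for completion time and for the acceptability ratings.

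**The concern.** The CM arm is paid for completing surveys, not for answering them accurately, while the stated purpose is better information for opioid prescribing. More surveys with less reliable content would work against that purpose, and the control arm is the means of checking. The one item that asks about rewards and accuracy is an uncontrolled self-rating, so the honesty item and survey-TLFB agreement are the only direct measures of accuracy available in both arms. Neither is turned into an arm difference.

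Printing two arm correlations side by side invites a comparison by eye, with two problems. The gap may be noise. It may also come from survey completion: a day of use can be counted in the survey total only if the survey covering that day was completed, and completion is what the intervention targets. A higher correlation in the CM arm could then be read as more accurate reporting when the arm has simply missed fewer days.

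**Working it through.** **1. The plan's own figure.** Sample Size Justification gives "32 participants/group are needed" for a two-sided *t*-test at "80% power, alpha level=.05 (Cohen, 1988"), with d = .711.

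- Normal approximation: n = 2(1.96 + 0.84)²/0.711² = 31.0, rounded up to 32. The exact *t* calculation gives 32.04, and power at 32 per group is 79.9%.
- Recruitment: 80 × 0.80 = 64, or 32 per group.

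The figure reproduces, but it concerns the primary *t*-tests. The documents give no planning figure for honesty or agreement.

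**2. Numbers available.** The Randomization paragraph prints 46 CM and 35 Co. At the plan's 80% retention: 46 × 0.8 = 36.8, about 37, and 35 × 0.8 = 28. The documents give no rate of 'very honest' answers, so 70-90% is assumed.

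**3. Precision of the honesty difference.** Half-width = 1.96 × √(p₁(1−p₁)/n₁ + p₂(1−p₂)/n₂).

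| 'Very honest', CM / Co | 37 / 28 | 46 / 35 |
|---|---|---|
| 70% / 70% | 22.5 points | 20.1 points |
| 90% / 90% | 14.7 points | 13.2 points |
| 75% / 90% | 17.8 points | 16.0 points |

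For 75% v 90% the difference is −15 points. The interval is −32.8 to +2.8 at 37/28 and −31.0 to +1.0 at 46/35. Both include zero.

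Contrasts detectable with 80% power at 37/28 are about 90% v 60%, 80% v 47% and 70% v 36%.

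**4. Precision of the raw correlation difference.** On Fisher's z scale with the Spearman variance 1.06/(n−3):

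- SE = √(1.06/34 + 1.06/25) = 0.271, so the half-width is 1.96 × 0.271 = 0.53.
- An observed .90 in one arm separates only from tanh(1.472 − 0.532) = .74 or lower in the other.
- An observed .80 separates only from tanh(1.099 − 0.532) = .51 or lower.

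**5. Completion alone can move the correlation.** Suppose everyone reports truthfully, missed surveys are unrelated to use, and completion is 60% for some and 90% for others (assumed).

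- A daily user has 28 TLFB days. Survey days are 28 × 0.6 = 16.8 at 60% completion and 28 × 0.9 = 25.2 at 90%: the same use and the same honesty, but different survey counts.
- A truthful person at 90% completion overtakes the 60% daily user once true use exceeds 16.8/0.9 = 18.7 days. So anyone using on 19 to 27 days ranks above a daily user on the survey and below on the TLFB.

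These rank reversals lower Spearman's coefficient without any inaccurate report. An arm with higher and more uniform completion has fewer of them. An interval on the raw difference would measure its noise but would not remove this effect.

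**The case against.** The strongest reply is that nothing stated goes unanswered. Aims 1 and 2 are worded as comparisons and carry hypotheses; Aim 3 only asks to examine agreement in each group, and within-arm estimates do that. This is a Stage I pilot whose declared main goal is effect sizes for the primary outcomes. That stands. The point is a cheap improvement, not the repair of a failed aim or of the primary analysis.

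A second reply is that Appendix B prints the honesty item among the acceptability questions, which are *t*-tested by arm. This does not hold: Table 4 lists honesty as an outcome separate from the 0-10 acceptability ratings, and Outcome Measures gives it its own descriptive analysis.

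Third, the honesty item is one self-rating, answered only by those who complete follow-up. An arm difference would mix truthfulness, readiness to admit dishonesty, and differential follow-up. This stands as a limit on interpretation.

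A reader might also infer that the plan will publish one pooled honesty figure that hides an arm difference: 75% of 37 and 90% of 28 would pool to about 81%. The text does not say so. Where the section means everyone together it says so, as in "The daily survey item responses will be summarized for the overall sample using descriptive statistics"; the honesty sentence is silent on arm. Nor does that sentence on daily items show that the arm completing more surveys will dominate, because it does not say whether records or participants are the unit.

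**Conclusion.** The concern holds as a gap in a secondary analysis. The plan collects two measures of reporting accuracy in both randomised arms and specifies no between-arm estimate for either. The correlations it lists by arm can also differ for reasons unrelated to accuracy.

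The achievable gain is modest. With 70-90% assumed 'very honest', the half-width is about 15-22 points at 37/28 and 13-20 at 46/35, so only large differences could be shown. It would be tempting to say that the trial could thereby demonstrate or rule out a loss of honesty under payment. The figures do not support that for a gap such as 75% v 90%, and a non-significant difference would not show that payment leaves reporting unchanged. Nothing in the documents indicates that payment does reduce honesty.

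These figures rest on the printed allocation, 80% retention in each arm and assumed honesty rates. The precision of matched-day agreement cannot be calculated from the documents, which give no agreement rates.

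**What to change.** 1. **Honesty.** State in Outcome Measures that the item is tabulated by arm, with the CM minus Co difference in the proportion 'very honest' and a 95% CI (Newcombe or exact). Label it exploratory and limited to follow-up respondents, and show the number responding in each arm.
2. **Survey-TLFB agreement.** Compute it only on days covered by a completed survey. Appendix A asks about the previous day, so each survey must be matched to the TLFB entry for the day before it was completed. Report the CM minus Co difference for alcohol and for opioids, with a 95% CI from a bootstrap that resamples participants. Name the agreement measure in advance; one option is each participant's proportion of matched days on which the two sources agree on use. Draw no conclusion from the separate arm correlations.
3. **Interpretation.** State that the intervals will be wide and that a null result is not evidence of no effect. Note also that the TLFB is itself self-report, and that matching days removes the counting artefact but not any selection in which days were surveyed.

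The cost is a few sentences and a few extra table rows with wide intervals. No new data are needed, provided the TLFB calendar entries are kept by day and not only as totals.

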**Table 4**

*Outcome Measures Overview*

Name	Time Frame	Brief Description
Number of daily surveys completed	28-day daily survey period	This primary outcome is consistent with previous CM studies.
Longest period of sustained adherence to daily survey completion	28-day daily survey period	Largest number of consecutive days wherein daily surveys were completed. This primary outcome is consistent with previous CM studies.
Mean frequency of alcohol and prescription opioid use (days of use)	28-day daily survey period to follow up	Spearman's correlations between daily survey and TLFB data for alcohol and prescription opioid frequency (days of use) were conducted for the entire sample, the CM group, and the Co group.
Mean time to complete the daily surveys	28-day daily survey period	Daily survey completion time (the amount of time from daily survey start to finish).

Name	Time Frame	Brief Description
Mean CM app feasibility and acceptability survey ratings	Follow up	CM app satisfaction, acceptability, and feasibility survey ratings (on a 0-10 scale; administered at follow-up) based on those used in a previous RCT investigating an app developed for chronic pain patients (Jamison et al., 2017).
Self-report validity and accuracy of responses	Follow up	Ratings of how honest participants were in completing the daily survey and how much the rewards made a difference in how accurately CM participants reported information in the daily survey.

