## Introduction

The opioid epidemic has spurred urgent and widespread legal, medical, and behavioral approaches to promote effective opioid prescribing. Between 21-29% of chronic pain patients misuse prescription (Rx) opioids (Vowles et al., 2015). Responsible opioid prescribing depends on accurate and early identification of misuse as well as comprehensive understanding of predictors of pain treatment seeking and successful pain management (Dowell et al., 2016). One promising and practical pain management solution is remote self-monitoring, a state-of-the-art assessment tool shown to be superior to retrospective assessment (e.g., Heron & Smyth, 2010). Unfortunately, low rates of adherence have impeded the use of remote self-monitoring among chronic pain patients (e.g., Jamison et al., 2016), even when non-monetary rewards were included (Jamison et al., 2017). One robust strategy for improving adherence is contingency management (CM). While CM has been widely used in research, translation to clinical practice has been limited, due to practical barriers (e.g., costs) and counselor concerns (e.g., Polak et al., 2020; Carroll, 2014).

This Stage 1 behavioral therapies development project (Rounsaville et al., 2001) will pilot test a novel, fully automated CM app (DynamiCare Rewards) for promoting daily self-monitoring of pain symptom severity and related variables (e.g., sleep, mood), as well as Rx opioid and alcohol use in a sample of chronic pain patients. This study is the first to customize the DynamiCare Rewards app to target survey completion, followed by a pilot controlled trial, comparing participants randomized to receive CM for completing daily self-monitoring surveys (CM group) or receive only electronic daily reminders to complete the survey (control group) over a 28-day period. Primary outcome measures include number of daily surveys completed and longest period of sustained adherence to survey completion. The study tested the hypothesis

that CM group participants will complete more daily self-monitoring surveys and will have a longer sustained period of daily survey completion compared to control group participants. Secondarily, the study examined feasibility; acceptability; and accuracy of Rx opioid and alcohol use reporting.

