## **Aims**

The specific aims of this Phase 1 therapy development project are to:

*Aim 1:* Compare number of completed daily self-monitoring surveys in CM and C groups. One hypothesis was tested:

*Hypothesis 1:* CM group participants will complete more daily self-monitoring surveys compared to control group participants.

*Aim 2:* Compare longest sustained period of daily survey completion in CM and C groups. One hypothesis was tested:

*Hypothesis 1:* CM group participants will have a longer sustained period of daily survey completion compared to control group participants.

*Aim 3:* Examine agreement between daily survey and follow-up visit reports of alcohol and Rx opioid use in CM and C groups.

*Aim 4:* Examine feasibility and acceptability of CM app implementation targeting self-monitoring of pain severity, related factors, and use of Rx opioids and alcohol.

*Aim 5:* Estimate effect-size to be used to perform power analyses and sample size calculations as part of the design of a larger RCT.

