**All Participants.** Day 1 of the daily surveys will start the day after the app is downloaded and the account is set up. Participants will be encouraged to complete the daily survey and pick a time of day to set a personal reminder. They will receive a text reminder around noon each day from a study smartphone. The daily survey data will automatically be uploaded to the DynamiCare HIPAA-compliant server. Participants' DynamiCare Rewards accounts will be manually archived after they completed the 28-day survey period.

**CM Group.** Participants randomized to the CM group will have the chance to receive incentives for complying with the target behavior (completing daily self-monitoring surveys within a 12-hour window (8am-8pm) over a 28-day period. Daily self-monitoring surveys and the delivery of incentives were completed using the DynamiCare Rewards app. The escalating variable-ratio reinforcement schedule used for the study was modeled after the fishbowl method developed by Petry et al. (2005a) and Olmstead and Petry (2009).

Behavioral incentives will be managed remotely via the app to facilitate extrinsic motivation for participant follow-through with self-monitoring. Participants will be able to draw from a fishbowl via the app to determine their monetary prize. Participants will be given an initial draw for downloading the app and completing training during the baseline call, which will be set to \$8. When they meet the target behavior, participants will be awarded additional draws through the app. The number of draws they earn will increase by one for every day they completed the survey. The maximum number of draws they could earn over the course of the 28-day period was 236. Failure to complete a daily self-monitoring survey, however, resulted in a reset to baseline (1 draw per completed daily self-monitoring survey) and 3 consecutive completed daily self-monitoring surveys will be required for a participant to return to the highest level achieved prior to reset. Additional engagement with the app will not result in additional monetary reinforcement.

***Incentives.*** Specifically, reward amounts ranged from \$0-50 in value. Half (50%) of incentives will be “good job” and not associated with a monetary reward. The app will be connected to reloadable debit cards (The Next Step debit card, provided by True Link Financial, Inc.), which will be activated and mailed to CM participants within one to two weeks of their baseline call.

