### ***Post-Daily Survey Period Follow Up***

At the end of the 28-day self-monitoring survey period, participants will be emailed a link to the REDCap follow-up survey (approximately 30-45 minutes), including The Brief Pain Inventory; Pain Self-Efficacy Questionnaire; Pain Catastrophizing Scale; Hospital Anxiety and Depression Scale; acceptability questions; Pittsburgh Sleep Quality Index; Timeline Followback (TLFB); and self-report validity and accuracy questions. If participants do not complete the survey within two days, they will be sent a reminder email. If participants do not complete the survey after three days, they will be called. Participants will be asked if they would like to be provided with a document summarizing their daily survey ratings in the follow-up survey. Once participants complete their participation in the study, we will remove their contact information from the study database to protect their privacy.

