## Appendix A

### **Daily Self-Monitoring Survey (via DynamiCare Rewards app)**

#### **How were you yesterday?**

1. What was your average pain? (rated on a 0-10 scale; 0=no pain, 10=worst pain)
2. How much did your pain interfere with your daily activities? (rated on a 0-10 scale; 0=did not interfere, 10=completely interfered)
3. Overall, how much have things changed? (rated on a 0-10 scale; -5=worse; 0=the same; 5=better)
4. How would you rate your sleep quality? (Very good (0) Fairly good (1) Fairly bad (2) Very bad (3))
5. How sad were you yesterday? (rated on a 0-10 scale; 0=not at all and 10=very much)
6. How anxious were you yesterday? (rated on a 0-10 scale; 0=not at all and 10=very much)
7. How irritable were you yesterday? (rated on a 0-10 scale; 0=not at all and 10=very much)
8. Did you take any prescription medications yesterday? (Yes or No)
9. [If yes to the above] Which prescription medications did you take? (check all that apply)
  - Prescription opioid pain reliever (for example: Percocet, Vicodin)
  - Prescription medication for anxiety or sleep (for example: Xanax, Ativan, or Klonopin)
  - Other prescription medication (free response)
10. [For those checked above] How did you take the [type of medication]?
  - Took as prescribed
  - Took less than prescribed
  - Took more than prescribed
  - It was not prescribed for me
11. How many 12-ounce beers containing alcohol did you have? (free response)
12. How many 5-ounce glasses of wine did you have? (free response)
13. How many shots of liquor did you have (straight or in a mixed drink)? (free response)
14. Did you use marijuana? (Yes or No)
15. Did you use cannabidiol (CBD)? (Yes or No)

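### Aim 3 correlates days of use counted only on completed surveys with days of use from a 28-day TLFB, so the per-arm correlation tends to be higher in the arm that completes more surveys, even if every report is truthful

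*Combined protocol and SAP*

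**What the plan says.** Under Aims, Aim 3 is to "Examine agreement between daily survey and follow-up visit reports of alcohol and Rx opioid use in CM and C groups". The Introduction describes the same secondary objective as "accuracy of Rx opioid and alcohol use reporting".

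The analysis appears in two places. The text under Outcome Measures plans Spearman's correlations for "Associations between daily survey and follow-up TFLB for alcohol and prescription opioid use data for the overall sample and each study group". Table 4 names the quantity: "Spearman's correlations between daily survey and TLFB data for alcohol and prescription opioid frequency (days of use) were conducted for the entire sample", followed by the CM group and the Co group.

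The two instruments cover days differently:

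- **Daily survey.** Appendix A heads it "How were you yesterday", so each survey records the day before. Under Baseline Visit Call, "Day 1 of the daily surveys will start the day after the app is downloaded and the account is set up". Each survey has an 8am-8pm window, and no later entry for a missed day is described.
- **TLFB.** Under Follow-Up Survey Only, "The TLFB was used to obtain detailed past 28-days frequency of opioid pain medication and alcohol use information". It is part of a follow-up survey whose link is emailed when the 28-day period ends. There is a reminder at two days, and then "If participants do not complete the survey after three days, they will be called". No closing date is given.

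The plan does not restrict the two sources to common dates, and it gives neither a denominator nor a rule for missed survey days.

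**The concern.** The survey total has a ceiling set by the number of surveys completed. The TLFB total has no such ceiling. Someone who used on 20 of the 28 days and completed half the surveys would show about 10 survey days against 20 TLFB days, with both instruments answered truthfully.

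This matters by arm because completion is what the intervention is meant to change. Missed surveys add noise to the ranking of participants on survey days: partly chance, because use days are lost at random, and partly because participants differ in how many surveys they complete. More missed surveys mean more noise and a lower Spearman correlation. If CM raises completion as hypothesised, its correlation tends to rise too.

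Whether paying for surveys affects the quality of what is reported is a real question in this trial; CM participants are asked it directly at follow-up. Read by arm, the planned statistic could credit incentives with better reporting when it has partly re-measured completion, or it could mask a real loss of accuracy in CM.

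**Working it through.** The plan states no figure for Aim 3 (no expected correlation, completion rate or power), so there is nothing to reproduce. The check asks what the planned statistic gives when nobody misreports.

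**Inputs from the plan.** Arm sizes are CM 46 and Co 35. Surveys fall on Days 1 to 28, each about the day before. The TLFB covers the past 28 days. The statistic is Spearman's rho on days of use within each arm.

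**Inputs assumed.** Completion rates; their spread between participants (beta distribution, concentration 3); the use patterns; and surveys missed at random with respect to use.

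**1. Expected survey count.** Expected survey days = completion × true use days. For users with a mean daily rate of 0.40, true days = 28 × 0.40 = 11.2.

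| Mean completion | Expected survey days |
|---|---|
| 90% | 0.90 × 11.2 = 10.1 |
| 75% | 0.75 × 11.2 = 8.4 |
| 60% | 0.60 × 11.2 = 6.7 |
| 50% | 0.50 × 11.2 = 5.6 |

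A uniform undercount alone would largely preserve ranks. The uneven loss across participants lowers rho. Simulating these users with truthful reports (a large sample per setting, TLFB window shifted by one day) gives rho of 0.97, 0.93, 0.86 and 0.76 at the four completion levels. With 40% never-users added, the range is 0.990 to 0.888.

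**2. Arm gap at the trial's sizes.** Mean rho over 600 simulated trials per setting, error-free reports, no TLFB delay, raw days of use:

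| Completion CM / Co | Alcohol-like (35% abstainers) | Opioid-like (45% none, 35% daily, 20% intermittent) | Use probability uniform on 0-1 |
|---|---|---|---|
| 75 / 65% | 0.963 − 0.939 = 0.024 | 0.948 − 0.934 = 0.014 | 0.857 − 0.796 = 0.061 |
| 85 / 60% | 0.980 − 0.923 = 0.057 | 0.959 − 0.928 = 0.031 | 0.912 − 0.767 = 0.145 |
| 90 / 50% | 0.987 − 0.892 = 0.095 | 0.966 − 0.911 = 0.055 | 0.940 − 0.705 = 0.235 |
| 70 / 70% | 0.952 − 0.951 = 0.001 | 0.941 − 0.941 = 0.000 | 0.825 − 0.828 = −0.003 |

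With equal completion the gap vanishes. If all participants within an arm share the same completion rate (85 / 60%), it is smaller but remains: 0.991 v 0.968, 0.971 v 0.962 and 0.980 v 0.937.

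**3. Proportion of completed days instead of counts.** Across the same unequal-completion settings, with and without TLFB delay, the gap falls to between 0.002 and 0.074.

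**4. Day offset and late TLFB.** Surveys on Days 1 to 28 cover Days 0 to 27. If the TLFB covers the 28 days before completion, a TLFB done on Day 28 + k covers Days k to 27 + k, and the overlap is 28 − k days: 28 on Day 28, 27 on Day 29, 25 on Day 31, 21 on Day 35. With every survey completed, rho is 0.998 for a 1-day shift, 0.992 for 4 days and 0.988 for 6. Delays spread evenly over 0 to 7 days leave rho at 0.989 to 0.999.

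**5. Same-date matching.** Restricting both sources to days with a completed survey that also lie in the TLFB window gives rho = 1.000 in both arms for all three use patterns (85 / 60%, delays 0 to 7 days). With perfect reporting this follows by construction, so the gaps in step 2 are purely a matter of coverage.

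**The case against.** **Raw counts are not spelled out.** Table 4 says days of use and gives no denominator. An analyst could use the proportion of completed days, which removes most of the gap. This stands as a limit on size. It does not answer the point, because days of use is the quantity named and a gap of up to about 0.07 remains.

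**Aim 3 is descriptive.** Aims 1 and 2 are framed as comparisons with hypotheses; Aim 3 is to examine agreement and has no hypothesis. A reader might infer that the trial will formally test accuracy between arms. The plan does not support that: it gives correlations overall and by arm, with no test between them. What remains is that two arm-specific values will stand side by side under an accuracy objective.

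**The direction is not guaranteed in one trial.** For the opioid-like pattern at 46 and 35 participants, Co equals or exceeds CM in about 22% of simulated trials at 85% v 60%, and in about 40% at 75% v 65%. Eligibility requires only one lifetime opioid prescription, so many participants may have no current use, which keeps the opioid gap small. This stands: the bias is a tendency, strongest for intermittent use (alcohol, or opioids taken as needed) with a large completion difference.

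**The day offset.** It is tempting to blame the survey's previous-day wording and late TLFB completion as well. Step 4 shows that they barely move Spearman's rho, and a TLFB done on Day 28 matches the survey days exactly. Lateness could favour an arm only if it differed by arm, on which the documents are silent. The TLFB form is not in Appendix B, so its calendar may already be tied to each participant's dates.

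**Conclusion.** The point holds for missed surveys. As Table 4 reads, the per-arm correlation depends on survey completion as well as on reporting, and completion is the outcome the intervention targets. With truthful reports throughout, the expected CM-minus-Co gap is about 0.01 at the low end, about 0.03 to 0.15 at 85% v 60% completion, and about 0.2 for intermittent use at 90% v 50%.

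These sizes rest on assumed completion rates, use patterns and random missingness, none of which the plan supplies. That a missed day drops out of the survey total is inferred from the absence of any catch-up entry or missed-day rule.

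The documents do not support the stronger conclusions that CM must look more accurate, or that the one-day recall offset drives an arm difference. The primary outcomes are unaffected. For a secondary aim of a Stage I pilot, the change is worth making because the per-arm values cannot otherwise be read as accuracy.

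**What to change.** 1. Pair the sources by calendar date: compare each completed survey on date d with the TLFB entry for d − 1.
2. Compute days of use in both sources over matched days only, and report Spearman's rho on those totals overall and by arm.
3. Add day-level percent agreement by arm, clustered by participant. Give kappa only as a supplement: it is unstable or undefined when use is nearly constant, as in never or daily users.
4. If the TLFB calendar is not already tied to each participant's dates, anchor it to the days the surveys cover (set-up day to Day 27).
5. Report use on unmatched days separately, with the number of matched days per participant by arm.

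**Cost.** A date merge at analysis and, if needed, a per-participant date setting in the REDCap calendar. Both instruments already collect use by day, so there is no added participant burden. Participants with few surveys contribute few matched days, and with an anchored calendar late responders recall a slightly older window.
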